1. INTRODUCTION

1.1. Indication

Maraviroc, in combination with other antiretroviral medicinal products, is indicated for treatment-experienced adult patients infected with only CCR5-tropic HIV-1 detectable.

1.2. Background and Rationale

1.2.1. HIV Infection: Epidemiology and Treatment

AIDS has killed more than 25 million people since it was first recognized in 1981, making it one of the most destructive epidemics in recorded history. As of December 2006, WHO/UNAIDS estimated that there were 39.5 million (34.1–47.1 million) people living with HIV/AIDS. 4.3 million (3.6–6.6 million) people were newly infected with the virus in 2005.¹

At present the only means of slowing HIV disease progression is the use of highly active antiretroviral therapy (HAART), with the preferred initial regimen containing a three or four-drug regimens consisting of a non-nucleoside reverse transcriptase inhibitor (NNRTI) or a ritonavir-boosted protease inhibitor (PI/r) plus two nucleoside reverse transcriptase inhibitors (NRTIs). Subsequent regimens frequently require more drugs, and become increasingly complex due to difficulty with adherence, tolerability due to adverse events and drug interactions with other required medications and the development of resistance to drugs in the failed regimen(s) or acquired resistant virus and class cross-resistance.²⁻⁴ In the developed world, where antiretroviral drugs have been available since 1987, the unmet medical need is for new antiretroviral medications with unique resistance profiles, improved short- and long-term safety profiles, and convenient dosing to treat patients who have not achieved treatment success with multiple treatment regimens due to drug resistance, side effects, incomplete adherence, or some combination of these factors. Drugs that target novel steps of the HIV-1 life cycle are needed, as they do not share cross-resistance with currently available antiretroviral therapy.

1.2.2. HIV Tropism

An essential, early step in the replication cycle of HIV-1 is attachment to the CD4 receptor and to one of the chemokine coreceptors, CCR5 or CXCR4. Generally, sexually transmitted HIV uses CCR5 exclusively during primary infection. However, HIV that can use CXCR4 to enter CD4+ T lymphocyte cells can be detected in about 15% of treatment naïve patients and up to 50% of patients with late HIV disease or antiretroviral treatment experience in the developed world where Clade B virus predominates. In most cases the CXCR4-using HIV (X4 HIV) is present with CCR5-using virus (R5 HIV) as a single virus that can use either receptor (dual tropic) or a mixture of R5 and X4 HIV (mixed tropic). Infections with HIV-1 that exclusively use CXCR4 to enter CD4+ T lymphocyte cells are rare, and represent approximately 1% of treatment naïve and approximately 2-4% of treatment-experienced patients.^{5,6}

1.2.3. CCR5 Antagonists

Maraviroc is a member of a new class of antiretroviral compounds known as small molecule CCR5 antagonists that block R5 HIV-1 entry into CD4+ T lymphocyte cells. This group of molecules binds non-competitively to CCR5, causing a conformational change in the extracellular loops of CCR5 that renders it unrecognizable to wild type R5 HIV-1.

1.2.4. Safety Concerns with CCR5 Antagonists

1.2.4.1. Hepatotoxicity

The development program for aplaviroc (GSK 873140), another CCR5 antagonist, was terminated due to severe drug-induced hepatotoxicity. For a third drug in this class, vicriviroc, no severe hepatic-related adverse events have been reported in the ongoing clinical trials to date.

The clinical data to date do not indicate that maraviroc causes abnormalities in hepatic function relative to placebo. No clinically relevant difference in severity or nature of hepatic dysfunction was observed among the two active and the placebo control treatment arms in the Phase 2b/3 program of maraviroc. There was a slight difference in rates of hepatic adverse events which was driven by events related to laboratory abnormalities but this difference was not evident when the overall laboratory data were analysed. Based on the available data, including those observed with maraviroc in short and long-term studies, it appears that the hepatotoxicity observed with aplaviroc is most likely drug-specific and not a class effect.

1.2.4.2. Infections and malignancies

When a CCR5 antagonist binds to the CCR5 receptor on the surface of CD4+ T lymphocyte, it blocks the natural function of the CCR5 molecule, which is primarily associated with retention of mononuclear cells in areas of inflammation and injury. Individuals who are born with two copies of a mutant CCR5 gene (CCR5 Δ 32) (ie, homozygous for CCR5 Δ 32) and do not express CCR5 on the surface of their CD4+ T lymphocyte cells represent 1% of Caucasians of European descent. They appear to be essentially resistant to HIV-1 infection and have apparently normal immune function. Individuals with one normal CCR5 gene and one copy of the CCR5 Δ 32 gene (ie, heterozygous for CCR5 Δ 32), who comprise 10-15% of Caucasians of European descent, have a reduced concentration of CCR5 molecules on the surface of their CD4+ T lymphocyte cells and have essentially normal immune function. Relative to HIV-infected patients with two copies of the normal gene, the CCR5 Δ 32 heterozygote individuals have delayed CD4+ T lymphocyte decline, delayed progression to AIDS, and longer survival once infected.⁷⁻¹⁰ However, whether blocking the CCR5 receptors in adults, who have had functioning CCR5 molecules throughout life, will have the same biologic effects as those observed in homozygotes or heterozygotes for CCR5 Δ 32 is unclear. It is theoretically possible that blocking CCR5 molecules after a critical period in immune development could result in increased or decreased immune surveillance, leading to increased frequency or severity of infections or malignancies.

090177e1928d33f51Approved On: 07-Jan-2020 12:23 (GMT)

Infection with West Nile Virus (WNV) is of particular scientific and clinical interest. Elderly and immunocompromised individuals have increased susceptibility to WNV, but genetic risk factors and immunologic control mechanisms have not been fully delineated. The monocyte and T lymphocyte chemokine receptor CCR5 have recently been identified as a key factor in viral clearance and survival in a mouse model of WNV encephalitis, in which the mechanism involved trafficking of leukocytes into the infected brain. Consistent with this, WNV induces expression of CCR5 ligands in WNV-infected mouse brain. To test whether this receptor is also protective in man, Glass and colleagues determined the frequency of *CCR5Δ32*, in two independent cohorts of patients, one from Arizona and the other from Colorado, who had laboratory-confirmed, symptomatic WNV infection.¹¹ The distribution of *CCR5Δ32* in a control population of healthy United States Caucasian random blood donors was in Hardy-Weinberg equilibrium and *CCR5Δ32* homozygotes represented 1.0% of the total group (n = 1,318). In contrast, *CCR5Δ32* homozygotes represented 4.2% of Caucasians in the Arizona cohort (odds ratios [OR] = 4.4 [95% confidence interval [CI], 1.6–11.8], P = 0.0013) and 8.3% of Caucasians in the Colorado cohort (OR = 9.1 [95% CI, 3.4–24.8], P < 0.0001). *CCR5Δ32* homozygosity was significantly associated with fatal outcome in the Arizona cohort (OR = 13.2 [95% CI, 1.9–89.9], P = 0.03). These authors concluded that CCR5 mediates resistance to symptomatic WNV infection. These findings may have important implications for the effect of CCR5-blocking agents on the incidence and severity of WNV infection.

On March 3, 2006 Schering-Plough announced that five cases of malignancy (four cases of lymphoma and one case of gastric adenocarcinoma) had been reported in 118 heavily pretreated patients participating in a Phase 2b clinical study of vicriviroc, AIDS Clinical Trial Group (ACTG) trial, A5211. The National Institute of Allergy and Infectious Disease (NIAID) Therapeutic DSMB overseeing the trial concluded that a causal association between vicriviroc and the lymphoma cases could not be established at that time. This experience is in contrast to findings of a 1999 article that reported a reduced risk of AIDS-associated lymphoma in HIV-infected *CCR5Δ32* gene heterozygotes when compared to individuals without the polymorphism.¹² Currently, the data from clinical studies in treatment-experienced HIV-1 infected patients do not indicate a clinically meaningful alteration in the frequency or severity of infections or malignancy related to the use of maraviroc. In the phase 2b/3 trials of maraviroc (MOTIVATE 1, MOTIVATE 2) at 48 weeks no difference in rates of lymphoma was demonstrated between maraviroc and placebo treatment arms, despite the much longer exposure in the maraviroc treated patients.

1.2.4.3. Myocardial Infarction

Metabolic abnormalities associated with HIV-1 infection, including glucose homeostasis disturbances and dyslipidemia, are increasingly prevalent, and there is concern about the possibility of an association with accelerated cardiovascular disease. In addition, recent results from the D:A:D Study, an international collaboration of 11 cohorts following 23,468 HIV-infected patients prospectively in 21 countries situated in Europe, the USA, and Australia, indicated that the incidence of myocardial infarction (MI) increased by 26% per year of exposure to combination antiretroviral treatment, consistent with the hypothesis that atherosclerosis is a side-effect of combination antiretroviral treatment, generally attributed to

PIs dosed simultaneously with NRTIs.¹³ The data from the Phase 2b/3 studies of maraviroc indicated a rate of MI and ischemic heart disease in keeping with that expected from the studied population. However there was an imbalance, with all the events occurring on maraviroc, most likely due to the design of the study and the limited follow up time in the placebo arm. Due to the relatively small data it is currently unknown whether the addition of maraviroc will modify the rate of MI occurrence in HIV-1 infected patients receiving HAART.

1.2.4.4. Rhabdomyolysis

Rhabdomyolysis is a condition associated with the injury of skeletal muscle. Rhabdomyolysis was initially described as a complication of traumatic injury particularly crush injuries however infections and most notably certain classes of drugs such as statins have been associated with this disorder. Myopathy has also been associated with nucleoside reverse transcriptase inhibitors (NRTIs), most notably zidovudine, which are commonly used in the treatment of patients with HIV. In the phase 2b/3 trials of maraviroc (MOTIVATE 1, MOTIVATE 2) subjects receiving maraviroc had a higher median change in creatine kinase compared to placebo. There was also a higher incidence of creatine kinase abnormalities (>2x ULN) in subjects receiving maraviroc: 30% and 29% on maraviroc QD and BID respectively, compared to 20% on placebo. Three patients in the MOTIVATE 1 and 2 studies reported adverse events of rhabdomyolysis or myositis and discontinued study drug. Two further patients receiving maraviroc QD in the MOTIVATE 2 study discontinued due to myalgia.

1.2.5. Study Rationale

There is limited information about the safety of long-term treatment with maraviroc. No signal for increased risk of hepatotoxicity, malignancy or infection has been observed in the clinical development program for maraviroc through 48 weeks of therapy. However, the concern that hepatotoxicity is a CCR5 antagonist class effect and the theoretical risk of altered immune function leading to altered rates or severity of malignancy or infections, including opportunistic infections (OI) remain to be fully addressed. Given the imbalance in the incidence of myocardial ischemic events in the ongoing clinical trials of maraviroc, data on long-term follow-up for MI and myocardial ischemia incidence in patients receiving maraviroc along with HAART would more fully characterize this potential safety risk. As most of these patients receive lipid-lowering agents that may be associated with a heightened risk of rhabdomyolysis, it is of interest to examine the incidence of this event. All-cause mortality will also provide information regarding any possible long term implications of treatment with maraviroc.

The objective of this international, multicenter, prospective observational comparative study is to monitor the safety of long term use of maraviroc in a larger and more diverse patient population than that in which the phase 2b/3 clinical trials were conducted. By providing additional data regarding long-term use of maraviroc, this study will help further characterize the safety profile of the drug. This is a post-approval safety study (PASS) and is a

commitment to the U.S. Food and Drug Administration (FDA) and the European Medicines Agency (EMA).

2. STUDY OBJECTIVES AND ENDPOINTS

2.1. Objectives

1. To estimate the incidence rates of: (a) Centers for Disease Control and Prevention category C AIDS-defining opportunistic infections (OI), (b) viral encephalitis, (c) liver failure, and (d) rhabdomyolysis in treatment-experienced HIV-1 infected patients receiving maraviroc during time of use and for up to six months following discontinuation of maraviroc treatment, up to a total of five years since entry into the study.
2. To estimate the incidence rates of (a) myocardial infarction (MI) or ischemia, (b) all malignancies, (c) all cause mortality, and (d) liver related deaths in treatment-experienced HIV-1 infected patients receiving maraviroc for up to five years after entry into the study regardless of the actual duration of maraviroc use.
3. To compare the rates of the study endpoints in patients receiving maraviroc to those observed in an internal comparator group of treatment-experienced, HIV-1 infected patients not receiving maraviroc.
4. To compare the observed rates of the study endpoints in patients receiving maraviroc in this study to those observed in HIV-1 infected patients not receiving maraviroc in an appropriate external comparator cohort (eg, EuroSIDA).

2.2. Endpoints

The study endpoints are:

1. Centers for Disease Control and Prevention Category C AIDS-defining opportunistic infections ([Appendix 1](#));
2. Viral encephalitis;
3. All malignancies;
4. Liver failure;
5. Myocardial infarction or ischemia;
6. Rhabdomyolysis;
7. Death from liver-related cause;
8. Death from any cause.

The operational diagnostic criteria of each endpoint are described in the endpoint adjudication manual for this study.

3. STUDY DESIGN

This is an international, multicenter, open-label, comparative, prospective observational epidemiologic study.

4. SUBJECT SELECTION

4.1. Study Population

The study will enroll 1500 HIV-1 infected, treatment-experienced adult patients who have been prescribed maraviroc along with an optimized background antiretroviral therapy (OBT) regimen in usual clinical practice following the approved local label of maraviroc.

The internal comparator group will consist of 1500 HIV-1 infected, treatment-experienced adult patients receiving OBT who received an HIV-1 tropism assay as a screening test for eligibility to receive maraviroc in usual clinical practice but were not prescribed maraviroc. This group may include patients infected with dual/mixed tropic or CXCR4 tropic HIV-1 as well as patients infected with CCR5 tropic HIV-1.

The subject enrollment scheme is presented in [Appendix 2](#).

The study will be conducted at approximately 300 sites in multiple countries. Participating countries were chosen on the basis of extensive feasibility assessments and include: Belgium, Brazil, Canada, France, Germany, Greece, Italy, Portugal, Spain, United Kingdom, and United States. If required, additional countries may be added and some countries in this initially proposed list may be dropped. Countries will participate only after maraviroc is approved by Health Authorities in that country and is commercially available. Enrollment will be competitive and recruitment of subjects will terminate after the global target sample size is achieved. The expected numbers of subjects in the participating countries are provided in [Table 1](#). Initial enrollment goals set for each country will be redistributed if necessary. Barring unforeseen circumstances (eg, significant delays in marketing authorization approval in countries, marked delays in regulatory approvals of the study protocol in countries, etc.), enrollment is expected to commence in 1Q2008 and is anticipated to continue for approximately 30 months. The enrollment status will be continuously monitored by the Sponsor and the external Scientific Steering Committee overseeing the study. If required, the enrollment period will be extended to enroll the necessary sample size.

090177e1928d33f51Approved/Approved On: 07-Jan-2020 12:23 (GMT)

Table 1. Enrollment targets by country

Countries	Expected number of study subjects	Projected launch date for commercial Maraviroc
Belgium	80	March 2008
France	200	April 2008
Germany	223	October 2007
Greece	40	March 2008
Italy	140	March 2008
Portugal	35	April 2008
Spain	250	May 2008
UK	161	November 2007
USA	1700	August 2007
Canada	80	October 2007
Brazil	91	May 2008

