4.2. Inclusion Criteria

Subjects (male or female) must meet the following inclusion criteria to be eligible for enrollment into the study:

1. The subject is antiretroviral treatment experienced and is currently being considered for treatment with maraviroc;
2. Receive an appropriate HIV-1 tropism assay as a screening for eligibility to receive maraviroc within 14 weeks prior to enrollment (The 14-week window does not apply to patients who started maraviroc as participants of A4001050 or A4001063);
3. Provide signed and dated informed consent to enrolling physician indicating that the patient (or, legally acceptable representative) has been informed of all pertinent aspects of the study;
4. Of 18 years of age or older (or, minimum age as determined by local regulatory authorities or as dictated by local law) at the time of screening;
5. Provide signed and dated informed consent to allow the enrolling physician access to medical, hospital and vital statistics records as appropriate;
6. Provide information on at least one alternate contact person (preferably the legal next of kin) who can be contacted regarding the patient's whereabouts and survival status, should the patient be lost-to-follow-up over the course of the study;
7. Acknowledge that in case of his or her death, the next of kin may be approached for a medical records release form if needed;

09017e1928d33f51Approved/Approved On: 07-Jan-2020 12:23 (GMT)

8. Provide Social Security Number (applicable to U.S. participants) or other national identification number or national health insurance number, as available and allowed by local law. **This information will only be used to search appropriate national or regional cancer and vital status registries for incidences of malignancies and deaths.**

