4.3. Exclusion Criteria

1. Pregnant or lactating;
2. Unable to provide informed consent;
3. Recipient of a small molecule CCR5 inhibitor other than maraviroc;
4. Previously enrolled in this study.
5. Already exposed to maraviroc (Except patients who started maraviroc as participants of either study A4001050 or study A4001063 and are still continuing the drug). These patients may constitute up to 15% of the target sample size in the maraviroc-exposed arm).

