7.2. Baseline Data

Once a patient has signed informed consent, baseline data will be collected at Screening and Enrollment visits. The enrolling physician will collect data from the patient interview and from relevant medical and laboratory records and will electronically complete baseline questionnaire pages without any personal identifiers. Data elements on the questionnaire pages will include but are not limited to:

- Study ID number;
- Date of birth;
- Sex;
- Race/ethnicity;
- Risk behavior(s) for HIV exposure;
- Duration of HIV infection;
- Diagnosis date and type of any current or past CDC category C AIDS-defining event;
- General medical history and relevant family history with specific emphasis on:
 - Malignancies: history of malignancies specifying the type and site;
 - Opportunistic infections: history of any opportunistic infection;
 - Past history of myocardial infarction (MI), ischemia and cardiovascular risk factors in general, including smoking history, family history and any significant EKG (ECG) finding if available;
 - History of any acute or chronic liver disease including viral hepatitis, alcoholic liver disease and alcohol use.
- Height, weight, systolic and diastolic blood pressure;
- Co-medications: including lipid-lowering agents, anti-hypertensive medication, anti-platelet medications, treatment for HCV/HBV, agents for OI treatment and prophylaxis and any potentially hepatotoxic medication;
- Components of OBT, including start dates and dose of each;

- Prior antiretroviral medication history with particular focus on the total duration of all antiretroviral therapy and number of failed regimens;
- Laboratory data: total, LDL and HDL-Cholesterol; serum triglycerides, liver enzymes: ALT, AST, bilirubin; Hepatitis B & C serology; CD4+ T lymphocyte cell count; nadir CD4+ T lymphocyte cell count; levels of HIV-1 RNA, HCV RNA from the most recent tests done per routine clinical care will be collected when available. During the screening and enrollment visits, historical data will be accepted for laboratory records up to 120 days prior to the visit date. (Please note: historical data on tests for viral hepatitis will be accepted up to 1 year prior to the visit date.) **There are no study mandated laboratory tests.**
- Result from the screening HIV-1 tropism assay;
- Starting date and dose of maraviroc;

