Appendix 3. Calculation of person-time expected to be accrued in the study

Scenario 1

Endpoints: All cause mortality, Liver-related death, Malignancies, Myocardial ischemia and infarction

Expected person-time of observation in maraviroc exposed and unexposed groups:

These events occurring at anytime during the 5-year follow up period will be adjudicated and analyzed as study endpoints. It is assumed that each year 10% patients will be lost to follow-up and that on average these losses will occur at the midpoint of the 12 months period.

Person-time accrual in the maraviroc exposed and unexposed groups for all cause mortality, Liver-related death, Malignancies, Myocardial ischemia and infarction				
	n at the beginning of period	Lost to follow-up midway of the period (provide 6 months of follow-up)	n at the end of the period (provide 12 months of follow-up)	Person-Years accrued
Year 1	1500	150	1350	1425.0
Year 2	1350	135	1215	1282.5
Year 3	1215	122	1093	1154.0
Year 4	1094	109	984	1038.5
Year 5	984	98	886	935.0
			Total person-years	5835.0

Based on the above assumptions, both these groups will accrue 5835 person-years of follow-up during the study for the assessment of all cause mortality, Liver-related death, Malignancies, Myocardial ischemia and infarction.

Scenario 2:

Endpoints: CDC category C AIDS-defining opportunistic infection, viral encephalitis, liver failure, rhabdomyolysis

Expected person-time of observation in:

These events will be adjudicated and analyzed as study endpoints if they occur during use of maraviroc or the anchor drug in the OBT, or within 6 months following their discontinuation

- Based on clinical experience, it is assumed that the rate of drug discontinuation will be higher in the earlier part of the study and will gradually decrease over time. To obtain a conservative estimate, it is assumed based on the observations from the 48-week clinical development program of maraviroc that the rate of discontinuation will be approximately 30% during the first 6 months of therapy, 25% between the 7th and 12th month, 20% between the 13th and 18th months and 15% in each 6 month

090177e1928d33f51Approved/Approved On: 07-Jan-2020 12:23 (GMT)

period thereafter. For the purpose of this calculation it is assumed that on average discontinuation occurs at the midpoint of each 6-month period.

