#### 4.2.3. Survival Bias

It is anticipated that up to 15% of the patients in the maraviroc-exposed group will comprise of patients who started maraviroc prior to enrollment in this study as participants in the maraviroc expanded access program (A4001050) and are still continuing the drug. The exact therapy start date and baseline covariates for these patients are documented in the A4001050 study database and will be used. Appropriate statistical analytical techniques (Muñoz, Wang et al. 1989; Hoover, Muñoz et al. 1991; Tarwater, Mellors et al. 2001; Cole, Li et al. 2004) that account for staggered entry of exposed subjects into study will be utilized to address the theoretical concern of survival bias from enrolling patients who were already exposed to the drug at study entry. In addition, sensitivity analyses will be performed to determine whether inclusion of such subjects substantially alters the findings of this study and the results will be reported.

The study will not enroll patients who started maraviroc in regular clinical practice outside of a clinical study since reliable data on the date of first exposure and baseline characteristics at that time may not be consistently available. Also, the study will not enroll into the maraviroc-unexposed arm any individual with prior exposure to maraviroc.

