
2
 
A patient who has received the Trofile™ assay within 8 weeks prior to screening:
 
If the result of the test is not yet available, the patient is eligible to be screened and enrolled and a repeat Trofile™ assay is not necessary. Please inform the patient about the study and obtain informed consent. When the result becomes available, enroll the patient in the appropriate study arm, enter the viral tropism in the CRF and fax the report from Monogram to Kendle.
 
If the test result is already available and shows a reportable HIV tropism (i.e., CCR5, CXCR4 or dual/mixed tropic) the patient is eligible to enroll provided he or she has not yet started maraviroc. Inform the patient about the study, obtain informed consent and enroll the patient in the appropriate study arm, enter the viral tropism in the CRF and fax the report from Monogram to Kendle.
 
If the test result was non-reportable, but based on your clinical judgment you still consider him a potential candidate for maraviroc and would like to repeat the tropism assay to get a reportable result, you can screen and enroll the patient. Please inform the patient about the study, obtain informed consent and send the sample to Monogram for the Trofile™ assay. Enroll the patient in the appropriate study arm when the result becomes available.
 
Kendle [contact]
	
4
 
A patient who is already exposed to maraviroc:
 
Patients who started taking maraviroc in the maraviroc expanded access program (EAP, A4001050) and are still continuing the drug at the time of screening will be eligible to enroll in POEM (A4001067). These patients will not need a repeat Trofile™ assay. Please inform the patient about the study and obtain informed consent. In the screening module of the CRF please complete the section on prior study participation with the relevant information. Please note that the FDA has allowed the inclusion of up to 300 such patients in A4001067 and we will inform you once that number is reached.
 
Patients who started maraviroc from any source other than the EAP (A4001050) are not eligible to enroll in POEM (A4001067). Please note that patients who started taking maraviroc in the Pfizer clinical trials A4001027 and A4001028 will be followed for long term safety under a separate program being run by Pfizer. These patients are not eligible to enroll in POEM (A4001067).

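### Most maraviroc patients are new starters, but comparators need not be starting their anchor drug, and the survival-bias provisions cover prior maraviroc use only

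*Protocol*

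**What the plan says.** **Entry, both arms.** Protocol 4.2 requires that "The subject is antiretroviral treatment experienced and is currently being considered for treatment with maraviroc", with a tropism assay within 14 weeks before enrollment.

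**Maraviroc arm.** Protocol 4.3 excludes anyone "Already exposed to maraviroc (Except patients who started maraviroc as participants of either study A4001050 or study A4001063 and are still continuing the drug"). It adds that "These patients may constitute up to 15% of the target sample size in the maraviroc-exposed arm". SAP Appendix 2 gives a count instead: "Please note that the FDA has allowed the inclusion of up to 300 such patients in A4001067".

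**Comparator arm.** Protocol 4.1 asks for "treatment-experienced adult patients receiving OBT who received an HIV-1 tropism assay as a screening test for eligibility to receive maraviroc" without a maraviroc prescription. Protocol 7.2 picks the anchor drug by a drug-class hierarchy, with no reference to when it was started. Under Protocol 7.4 and SAP 6.1, adjudication of opportunistic infections, viral encephalitis, liver failure and rhabdomyolysis ends six months after maraviroc (exposed) or the anchor drug (comparator) is stopped.

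**Survival bias.** SAP 4.2.3 promises staggered-entry methods and sensitivity analyses against "survival bias from enrolling patients who were already exposed to the drug at study entry". Both concern patients who began maraviroc before entry. Its only prior-use rule for comparators is that they must not have taken maraviroc. SAP 8.2 item 7 refers back to this section.

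**Planning.** Appendix 3, Scenario 2, assumes for both arms that "the rate of discontinuation will be approximately 30% during the first 6 months of therapy", with lower rates later, and arrives at 2,875 person-years per arm.

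**Data.** Protocol 7.2 collects "Components of OBT, including start dates and dose of each". No analysis that uses the start dates is described.

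**The concern.** For the four drug-window endpoints the anchor drug is the comparator's counterpart to maraviroc, because it sets how long events count. The plan accepts that patients already taking the drug at entry can distort a rate, and it deals with this in the maraviroc arm by exclusion, a cap, special methods and a sensitivity analysis. It has no parallel provision for a comparator who entered after a tropism assay but stayed on an anchor drug begun long before.

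If event rates differ between the first months of a regimen and later, the arms would then differ in time on treatment as well as in drug. Time on the anchor drug is not among the covariates named in SAP 6.2, so the propensity score need not balance it. Objective 3, the internal comparison, could show a rate ratio away from 1 with no maraviroc effect, and the plan gives the reader no means of telling how much of the ratio comes from this.

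**Working it through.** **New-starter share of the maraviroc arm.** Protocol 4.3: 15% of 1,500 = 225 roll-overs, so at least 85% new starters. SAP Appendix 2: 300/1,500 = 20%, so at least 80%. (300 is 15% of 2,000, the exposed-arm target before the change recorded in SAP Section 1.)

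**Reproducing the planned person-time.** Inputs from Appendix 3, Scenario 2: 1,500 patients; discontinuation of 30%, 25%, 20%, then 15% per 6-month period; 5% lost per period at mid-period; 6 months of observation after stopping.

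- Each period, those on drug contribute 0.5 × 0.95 + 0.25 × 0.05 = 0.4875 years each. Patients who stopped in the previous period contribute a further 0.25 years.
- First period: 1,500 × 0.4875 = 731.25 person-years.
- Ten periods: 2,898 person-years, against the stated 2,875 (0.8% higher). Other ways of counting losses give 2,804 to 3,156.
- First-6-month share: 731.25/2,898 = 25%.

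**If every comparator were established.** With the plan's own later rate of 15% per period from entry, the same table gives 3,588 person-years, 24% more (3,588/2,898 = 1.238).

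**Illustrative bias with no true drug effect.** Two quantities are assumed because the documents do not give them: k, the ratio of the event rate in the first 6 months of a regimen to the later rate, and f, the share of an arm already established at entry. Taking the later rate as 1:

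- New starters: person-years 2,897.8; events 731.25k + 2,166.5, which is 3,629.0 for k=2 and 4,360.3 for k=3.
- Established patients: person-years 3,588.0; events 3,588.0.
- Arm rate(f) = [(1 − f) × new-starter events + f × 3,588.0] / [(1 − f) × 2,897.8 + f × 3,588.0].
- Apparent rate ratio = rate(maraviroc f) / rate(comparator f).

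Worked case, k=3, maraviroc f = 0.15, comparator f = 0.50:

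- Maraviroc: (0.85 × 4,360.3 + 0.15 × 3,588.0)/(0.85 × 2,897.8 + 0.15 × 3,588.0) = 1.414.
- Comparator: (0.5 × 4,360.3 + 0.5 × 3,588.0)/(0.5 × 2,897.8 + 0.5 × 3,588.0) = 1.225.
- Ratio: 1.154.

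| k | Roll-overs, uncorrected | Comparators established: 0% | 25% | 50% |
|---|---|---|---|---|
| 2 | 15% | 0.964 | 1.024 | 1.085 |
| 3 | 15% | 0.940 | 1.042 | 1.154 |
| 2 | none | 1.000 | 1.063 | 1.125 |
| 3 | none | 1.000 | 1.109 | 1.228 |

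A simpler version gives new starters and established patients equal person-time and takes the early share as 731/2,875 = 0.254. For k=3 the new-starter rate is 0.254 × 3 + 0.746 = 1.508, and a comparator arm with 50% established has 0.5 × 1.508 + 0.5 = 1.254. The ratio is 1.508/1.254 = 1.20 with no roll-overs, and (0.85 × 1.508 + 0.15)/1.254 = 1.14 with 15%.

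**Benchmark.** Table 2 gives a detectable relative rate of 1.1955 for opportunistic infections.

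**The case against.** The strongest counter-argument is the common entry point. Both arms enter while maraviroc is under consideration, with a recent tropism assay, so a change of regimen is in view for every patient and many comparators may be starting new drugs. This stands: the documents do not show that long-established comparators are common. They do not rule them out either, and no planned summary would reveal the number.

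The direction is also open. A reader might infer that established comparators have passed their early toxicity and early failure, so that the rate ratio must be inflated. The documents do not support that. A treatment-experienced patient established on a drug yet considered for maraviroc may be failing it. In the k=2 case with 15% roll-overs and 50% established, suppose the established comparators' rate is r times the later rate. The ratio equals 1 when r = (1.2071 × 3,242.9 − 1,814.5)/1,794.0 = 1.17; above that it falls below 1. Screening HIV-1 RNA and CD4+ count, which reflect current failure, are already covariates.

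A reader might also take the shared discontinuation curve in Appendix 3 as an error. The protocol calls it conservative and derives it from maraviroc's own program. Established comparators would add person-time and events together, which does not by itself bias a rate. What remains is that the planned equality of person-years rests on a symmetry that eligibility does not secure.

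Finally, SAP 6.2 allows other relevant covariates, and SAP 8.2 item 4 allows subgroups by total antiretroviral duration and background components. Neither commits to using time on the current regimen.

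**Conclusion.** The concern holds as a gap in the analysis plan. Entry by time on drug is controlled in one arm only, and the survival-bias provisions follow that same arm. It bears mainly on the four drug-window endpoints. For the other four of the eight, SAP 4.2.2 counts follow-up regardless of how long the anchor drug is used, so the anchor drug does not set the window.

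The size is illustrative and rests on assumed k and f. With 15% uncorrected roll-overs and 25% to 50% of comparators established, the apparent ratio is 1.024 to 1.085 for k=2 and 1.042 to 1.154 for k=3, all below the 1.1955 in Table 2. A reader might infer that the bias matches the detectable effect for opportunistic infections. At k=3 and 50% established, that happens (1.20, or 1.23 with life-table weighting) only if roll-overs are excluded or fully corrected. Nor do the documents establish that new starters are in fact being compared with survivors; they only leave it possible. This is a cheap improvement to make, not a flaw that invalidates the comparison.

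**What to change.** In SAP 4.2.3:

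1. Use the background-regimen start dates already collected to report, by arm, how many patients are established and how many are on a new regimen at entry. Define a new-regimen comparator as one with an anchor drug or other background component started at or after the screening tropism assay. The anchor drug alone is not enough, because the hierarchy could label as established a patient who keeps raltegravir but newly starts darunavir.
2. Prespecify a sensitivity analysis of Objective 3, at least for the four drug-window endpoints, comparing maraviroc patients who are not roll-overs with new-regimen comparators.
3. Add a second version that classifies comparators by the anchor-drug start date alone.
4. Define roll-overs to match Protocol 4.3, which admits patients from A4001063 as well as A4001050; SAP 4.2.3 names only A4001050. Reconcile the 15% cap with the 300-patient figure.

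The cost is SAP text and two restricted analyses. They will have fewer comparator events and wider intervals, so they should be read as a check on the main result. Eligibility and data collection do not change.
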